4.2. Dose Justification

4.2.1. Human Predictions

4.2.1.1. Prediction of Human Pharmacokinetics

The PK data from cynomolgus monkeys were characterized using a 2-compartmental model incorporating linear and non-linear clearance (V_{\max}/K_m model), to describe the observed non-linear PK. Subsequently, a human PK model was established by allometrically scaling the PK parameters from monkey to human. The scaling was performed to be the most conservative (produce the highest exposure) by using scaling factor of 0.75 for V_{\max} and 1 for K_m . In humans the projected serum CL and V_{ss} for the linear process were 0.11 mL/hr/kg and 87 mL/kg respectively, and the parameters for non-linear clearance mechanism (V_{\max} and K_m) were predicted to be 385 $\mu\text{g}/\text{kg}/\text{hr}$ and 942 nM, respectively. The terminal half-life was estimated to be approximately 8-9 days.

4.2.1.2. Prediction of Human Efficacious Exposure

The data obtained from the pharmacology study in a CIA mouse model were fitted using a direct effect I_{max} model where either average concentration (C_{av}) or trough concentration (C_{min}) were assumed to drive the response (% normalized disease score). The human efficacious concentration (C_{eff}) was defined as the C_{av} or C_{min} to achieve the expected IC_{90S} in human, which was calculated based on the mouse IC_{90S} after correcting for the mouse-human potency difference. The potency correction was based on the in vitro $Fc\gamma RIIB$ and $Fc\gamma RIIIA$ binding assays, which suggests a more than 10x higher binding avidity for human $Fc\gamma RIIB$ and $Fc\gamma RIIIA$ compared to mouse. The projected C_{eff} is 37 $\mu g/mL$ for C_{av} (or 6 $\mu g/mL$ for C_{min}).

4.2.1.3. Clinical Dose Selection

4.2.1.3.1. Intravenous Administration in Healthy Participants

The starting dose of PF-06755347 proposed for this study was 0.01 mg/kg (IV). Subsequent dose escalation was to proceed to either the highest dose deemed to be well tolerated with an acceptable safety profile or the achievement of plasma exposure equivalent to the PK stopping limits. The PK stopping limits proposed in this study were chosen based on the Day 36 exposures of PF-06755347 achieved at the NOAEL (50 mg/kg weekly) from the 6-week lower dose range monkey toxicity study (see Section 2.2.3). Human PK parameters and efficacious exposure predicted for PF-06755347, along with the toxicokinetic data, and anticipated binding and pharmacological activity, were used to establish the dose range to be studied. The dose range in this study aimed to bracket the expected clinically efficacious exposure range in humans, while allowing for uncertainty in the prediction of targeted efficacious concentration and PK.

Table 6. Observed Human Exposure and Safety Margin Following Single IV Administration of PF-06755347

Dose (mg/kg)	Human Exposure of Plasma PF-06755347 ^a		Observed Safety Margin ^b	
	C_{max} ($\mu g/mL$)	AUC_{168} ($\mu g \cdot hr/mL$)	C_{max}	AUC_{168}
0.01	0.112	1.41	10089	24113
0.03	0.446	10.5	2534	3238
0.1	1.65	45.2	685	752
0.3	4.70	139.0	240	245
0.7	12.4	281.0	91	121
1	24.7	490.0	46	69

a. C_{max} and AUC_{168} are observed exposure levels following IV administration. Please refer to Investigator's Brochure for additional details.

b. Safety margins for C_{max} and AUC are calculated using the exposure limiting criteria (NOAEL in lower dose range monkey toxicity study: $C_{max} = 1130 \mu g/mL$ and $AUC_{168} = 34000 \mu g \cdot hr/mL$); and equal to the ratio of limiting criteria/observed C_{max} or AUC_{168} .

The starting IV dose of 0.01 mg/kg was projected to be safe with anticipated level of Fc-gamma receptor occupancy estimated at 1% and minimal associated pharmacological activity. Non-clinical human pharmacology and non-human primate (NHP) toxicology studies suggested that this dose would achieve greater than 5000-fold safety margin over the NOAEL, and would not be associated with any clinical symptoms or vital sign changes. The dose was predicted to be associated with low level transient systemic IL-6 release, but was

not expected to be associated with elevated levels of other cytokines or with any evidence of complement activation.

The observed C_{\max} (0.112 $\mu\text{g/mL}$; [Table 6](#)) at the starting IV dose was approximately 10-fold lower than the C_{\max} achieved at the lowest dose level tested in the 6-week pivotal toxicity study in cynomolgus monkeys (0.1 mg/kg, 1.77 $\mu\text{g/mL}$), and was similar to the C_{\max} on Day 1 of the investigative monkey study (8384439/18GR088) at the 2 lowest doses tested of 0.005 (0.097 $\mu\text{g/mL}$) and 0.01 mg/kg (0.168 $\mu\text{g/mL}$). All doses, 0.005, 0.01 and 0.05 mg/kg, produced minimal transient elevations in IL-6 but not in TNF α or INF α or complement. This IL-6-only response at ≤ 0.05 mg/kg was less than that observed at 0.1 mg/kg in monkeys, where non-adverse, minimal changes in cytokine and complement activation products were observed. There were no effects on immune cells, or changes in clinical signs, other laboratory parameters or macroscopic and microscopic observations at 0.1 mg/kg in monkeys. Minimal changes in heart rate were observed at 0.1 mg/kg in NHP, with no other hemodynamic changes (more details can be found in the accompanying IB). Thus the safety data package supports the choice of the proposed starting dose of 0.01 mg/kg.

A receptor occupancy calculation was also performed. Since PF-06755347 binds to multiple Fc γ Rs on multiple cells, the apparent K_d was determined using in vitro human whole blood. PF-06755347 exhibited the greatest binding avidity towards B cells, with an apparent K_d of 13.95 $\mu\text{g/mL}$. Using this most conservative apparent K_d value, the predicted peak receptor occupancy achieved at the starting dose of 0.01 mg/kg was expected to be approximately 1%, which also represents an EC_3 for in vitro IL-6 release in human whole blood, the most sensitive functional assay.

Furthermore, the 0.01 mg/kg starting dose is 1/200,000th of the prescribed loading dose of 2 g/kg for IVIg (based on Gamunex[®]-C US prescribing information [USPI]⁹ for CIDP) on a mg/kg basis (or 1/200th to 1/2000th of an estimated loading dose of IVIg, if corrected for the approximately 100-1000x higher human Fc γ R binding avidity for PF-06755347 vs. IVIg).

Dose escalation beyond the starting dose will be dictated by the criteria summarized in [Section 6.7](#) and will aim to occur in incremental increases of no more than half-log (ie, 3.3 fold) based on predicted exposure, with smaller increments if required due to emerging safety data or once the expected PF-06755347 exposure approaches the PK stopping limit. The actual doses to be evaluated in the escalation sequence as well as the number of dose levels to be evaluated may be adjusted according to emerging safety, tolerability and PK data, provided the dose escalation criteria specified in [Section 6.6](#) and [Section 6.7](#) are not violated. These criteria are applicable to both IV and SC administration.

A body weight-based dosing approach (mg/kg) was used in this study for the IV cohorts with the goal of reducing inter-individual variations in IV infusion/dosing rate and PK exposure. PF-06755347 was administered as a single infusion over 60 minutes for the starting dose of 0.01 mg/kg. Based on emerging safety data of cytokine elevation at the 1 mg/kg dose level, the infusion duration was increased to 3 hours for an expansion cohort at 1 mg/kg. ([Section 6.1.1.1](#)). The increase in infusion duration was expected to modulate the tolerability of PF-06755347. Safety data from the 1 mg/kg expansion cohort showed that an increase in

infusion duration to 3 hours did not modulate the tolerability profile of PF-06755347 and subsequently, the next cohort used 0.7 mg/kg infused over 1 hour. Guidelines for the proposed infusion rate at each dose level are provided in [Section 6.1.1.1](#). However, the actual dosing rate could have been reduced and/or the overall infusion time increased at the discretion of the PI and upon the review of the available safety data. The overall infusion time was not to exceed 4 hrs. If deemed appropriate by the PI, concomitant medications (such as acetaminophen and diphenhydramine) coupled with adjustment of dosing rate could have been implemented to manage possible emerging symptoms that may have been related to transient pro-inflammatory activity.

4.2.1.3.2. Subcutaneous Administration in Healthy Participants

Following IV administration of PF-06755347, the observed safety data to date has shown Grades 1 and 2 CRS associated with IV doses of 1.0 and 0.7 mg/kg, respectively. Cytokine (eg, IL-6) elevation peaked within the first few hours following IV administration and returned to baseline levels within 24 hours. These results may suggest that the degree of cytokine release is dose dependent and potentially correlated with PF-06755347 C_{max} and the rate of rise to achieve C_{max} . SC dosing of PF-06755347 offers the potential to blunt the severity of CRS by reducing the C_{max} and delaying the time to achieve C_{max} (T_{max}). The observed C_{max} (0.895 $\mu\text{g/mL}$) at the proposed starting SC dose of 25 mg is approximately 5-fold lower than the observed mean C_{max} (4.7 $\mu\text{g/mL}$) achieved at the highest tolerated IV dose level of 0.3 mg/kg ([Table 6](#)), with a safety margin of 1263 for C_{max} and 345 for AUC_{168} . Observed C_{max} values in subsequent dose levels of 50 and 100 mg were of 1.37 and 2.64 $\mu\text{g/mL}$ respectively; approximately 3.5-fold and 1.8-fold lower than the values observed at the 0.3 mg/kg IV dose level. The SC dose level of 300 mg will only be explored when SC doses up to 200 mg levels are deemed to be safe and well tolerated and within the PK stopping limit criteria.

In order to support subcutaneous delivery of PF-06755347, a toxicology study (Study 14MA141, IB Section 5.3.7) in NHP was conducted with a single 250 mg/kg SC dose and the results showed that the drug was tolerated.

The dose for the optional Japanese SC Cohort 12, if conducted, will be the highest dose from Cohorts 7-11 that is found to be safe and well tolerated.

Table 7. Observed/Predicted Human Exposures and Safety Margins Following Single SC Administration of PF 06755347

Dose (mg) ^a	Human Exposure of Plasma PF-06755347		Safety Margin ^b	
	C _{max} (µg/mL)	AUC ₅₇₆ or AUC ₁₆₈ (SC) (µg·hr/mL)	C _{max}	AUC
25 mg SC ^c	0.895	98.5	1263	345
50 mg SC ^c	1.37	159	825	214
100 mg SC ^c	2.64	315	428	108
200 mg SC	5.28	630	214	54
300 mg SC	7.92	945	143	36

- Depending on the safety and PK data available, dose escalation may be adjusted to doses other than those outlined above while following dose progression and stopping rules outlined in [Section 6.6](#) and [Section 6.7](#).
- Safety margins for C_{max} and AUC are calculated using the exposure limiting criteria (NOAEL in lower dose range monkey toxicity study: C_{max} = 1130 µg/mL and AUC₁₆₈ = 34000 µg·hr/mL); and equal to the ratio of limiting criteria/projected C_{max} or AUC₁₆₈ or AUC₅₇₆ (SC).
- Observed exposures and safety margins are reported for 25 mg, 50 mg and 100 mg SC dose.

4.2.1.3.3. Subcutaneous Administration in Participants with ITP

The starting dose of the ITP cohorts will be dependent on the equivalent dose levels in healthy participants having been studied and been deemed to be safe and well tolerated.

The dose levels to be tested in participants with ITP may include SC doses of 25 mg, 50 mg or 100 mg. The observed mean C_{av} after administration of a single 25 mg SC dose in HP was 0.586 µg/ml. This C_{av} is approximately 2-fold higher than the C_{av} of 0.25 µg/ml for ≥90% receptor occupancy for human FcγR. Thus it is expected that the lowest proposed dose in participants with ITP in this study could have pharmacological activity after a single dose.

The starting dose for participants with ITP will be 25 mg based upon the safety and tolerability data in HP.

Dosing progression and escalation are outlined in [Section 6.6](#) and [6.7](#).

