Clinical tolerability, safety, PK, CCI [REDACTED] data will be reviewed by a dose escalation subteam to establish whether each dose level is considered safe and well tolerated. These criteria may lead to a pause to evaluate participants at a given dose level, to repeat a dose, or to dose escalation. Unless a specific pause criterion is met, a review of all available safety, PK, cytokine and complement data will occur after each cohort has completed and dose escalation will proceed if the last dose was considered to be well tolerated. In the event of dosing pause, all available safety, cytokine, and complement data for the participants will be reviewed by the dose escalation subteam. The subteam should determine whether clinical signs and symptoms, including laboratory findings, associated with the pause criteria have resolved and whether it is safe to continue dosing.

Data Monitoring Committee:

This study will not use an external data monitoring committee. However, the dose escalation subteam will include an external Sponsor-independent safety reviewer.

Statistical Methods

No formal inferential statistics will be applied to the pharmacokinetic data.

The plasma concentration of PF-06755347 will be listed and summarized descriptively by nominal PK sampling time and treatment group. Individual participant, mean and median profiles of the plasma concentration time data will be plotted by treatment group using actual and nominal times, respectively. Mean and median profiles will be presented on both linear and log scales.

Baseline and change from baseline in cytokines and complement components will be summarized descriptively and plotted by dose.

Platelet counts for participants in the ITP Cohorts will be listed and summarized descriptively as absolute values and change from baseline.

[figure not shown]
Immunogenicity (anti-drug antibody [ADA]) results will be listed (including titers) and summarized by treatment group and time points. Participant level immune response will also be summarized by treatment. Effect of positive ADA on safety, PD and PK will be assessed, if appropriate.

CCI [REDACTED]

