2.1. Study Rationale

The current study is the first clinical trial with PF-06755347. It is designed to evaluate the safety, tolerability, PK and CCI following IV infusion and SC injection to healthy adult male participants and SC injection in adult male or female participants with persistent or chronic primary ITP.

Platelet count response in ITP is a robust, objective, validated biomarker for efficacy for IVIg. An increase in platelet count would be informative for the clinical development of PF-06755347 in ITP and CIDP. Participants with persistent and chronic primary ITP are chosen to ensure a low likelihood of spontaneous resolution of the platelet count. Participants with moderate to severe ITP ($30 - 75 \times 10^9$ platelet count) who have no acute need for therapy are selected to minimize undue risk to the participant (see IB, Section 6.2.1.1), including bleeding at the injection site.

PF-06755347 modulates the production of pro- and anti-inflammatory cytokines and the production of complement activation products in vitro and in nonclinical species. A maximum tolerated dose of 0.3 mg/kg by intravenous infusion has been identified, with Grades 1 and 2 CRS observed at higher doses of 0.7 and 1 mg/kg. No further IV dosing will occur. (see Investigator Brochure Section 6.2). Moving forward, the safety, tolerability, and PK of PF-06755347 will be assessed following SC administration.

In ITP, bleeding may occur due to low numbers of platelets, circulating cell fragments that clump together to form plugs in blood vessel injuries.

The study design with single escalating IV and SC doses of PF-06755347 is ongoing with review of safety, PK and CCI. To permit an unbiased assessment of safety, the administration of active PF-06755347 versus placebo in each healthy participant cohort will be double-blinded to site staff (except those involved in preparation of doses) and participants. All participants in the ITP cohorts will receive PF-06755347. To allow for real-time review of the safety, tolerability, PK and cytokine/complement data, a designated limited number of Sponsor colleagues will be unblinded, with careful measures exercised to limit degree of unblinding. Refer to [Section 9.9](#) for details. An independent and medically qualified reviewer, external to Sponsor and with authority to pause dose escalation to the subsequent cohort, will also be included as an unblinded member of the dose-escalation subteam.

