2.3. Benefit/Risk Assessment

PF-06755347 is not expected to provide any clinical benefit to healthy participants but it may provide a transient increase in platelet count in participants with persistent or chronic ITP. This study is designed primarily to generate safety, tolerability, and pharmacokinetic data that will support further clinical development.

PF-06755347 has been shown to cause transient elevation in pro-inflammatory cytokines. Symptoms associated with CRS vary greatly and may be difficult to distinguish from other conditions. The more common symptoms include fever, nausea, headache, tachycardia, hypotension, rash and shortness of breath. The severity of symptoms can be mild to life threatening and thus there should be a high suspicion for CRS if these symptoms occur. Cytokines will be analyzed to determine if cytokine elevation consistent with CRS is observed (see [Section 10.10](#)). The severity of CRS will be assessed according to the most

recent consensus grading from the American Society for Transplantation and Cellular Therapy (ASTCT).²

For study participants with ITP, there is an increased risk of procedure-related bleeding/bruising from subcutaneous injections, mitigated by the lower bound of platelets in the eligibility criteria. An increased risk of thrombosis has also been reported in ITP.¹⁵ High dose single IV administration of PF-06755347 may transiently lower platelet counts in healthy participants, while repeat IV administration in non-clinical studies may also lower platelet counts. The predicted C_{max} with SC administration in ITP participants is approximately 6 fold lower than observed C_{max} at 1 mg/kg at which the reduction in platelet count was observed in healthy participant (see [Table 6](#)). More detailed information about the known and expected benefits and risks and reasonably expected adverse events of PF-06755347 may be found in the investigators brochure, which is the SRSD for this study.

Each study site should have a COVID-19 risk mitigation policy (RMP), which documents the site's COVID-19 virus testing strategy for participants and staff, social distancing measures, and management of COVID-19-like symptoms.

To account for the widespread deployment of COVID-19 vaccine during the COVID-19 pandemic, the benefit/risk analysis has assessed both the impact of PF-06755347 on risk of COVID-19 disease in study participants who may become infected with SARS-CoV-2 and the efficacy of COVID-19 vaccines.

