8.3.8.1. Lack of Efficacy

This section is not applicable because efficacy is not expected in the study population.

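### Does the ITP dose rationale contradict the protocol's own projected efficacious exposure, so that a flat platelet response could not be read?

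*Protocol*

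**What the plan says.** Protocol section 4.2.1.2 fits a mouse collagen-induced arthritis model, corrects for the mouse-to-human potency difference and states a target: "The projected C_{eff} is 37" µg/mL as an average concentration, or 6 µg/mL as a trough. Section 4.2.1.3.1, on IV dosing in healthy participants, adds that "The dose range in this study aimed to bracket the expected clinically efficacious exposure range in humans".

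Section 4.2.1.3.3, on SC dosing in ITP, uses another yardstick. It compares the observed average of 0.586 µg/mL at 25 mg SC with 0.25 µg/mL, the level "for ≥90% receptor occupancy for human FcγR". It concludes that the lowest dose could be pharmacologically active. It mentions neither 37 nor 6 µg/mL and names no assay. For the other ITP doses, section 4.2.1.3.2 reports that Cmax "values in subsequent dose levels of 50 and 100 mg were of 1.37 and 2.64" µg/mL.

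On platelets, section 2.1 says "An increase in platelet count would be informative for the clinical development of PF-06755347 in ITP and CIDP". Section 2.3 says of the drug that "it may provide a transient increase in platelet count in participants with persistent or chronic ITP". Section 8.3.8.1 reads "This section is not applicable because efficacy is not expected in the study population". The planned analysis is in the synopsis: "Platelet counts for participants in the ITP Cohorts will be listed and summarized descriptively as absolute values and change from baseline". Section 9.1 rules out hypothesis testing, and section 9.4.1 says an efficacy analysis does not apply.

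**The concern.** A dose rationale normally carries one expectation of activity through to the interpretation of the data. Here there appear to be two, pointing in opposite directions. Against 0.25 µg/mL, the ITP doses look close to receptor saturation already at 25 mg. Against 37 µg/mL, they look 20- to 63-fold too low, and even their peak concentrations fall short of the 6 µg/mL trough target.

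With no placebo and 3 to 6 participants in each of Cohorts 13 and 14, the meaning of an absent platelet rise would seem to depend on which benchmark the reader holds. On the first, it would count against the mechanism, and little separation between doses would be expected. On the second, it would say little, and a dose trend would be expected. Section 9.9 allows the data to support PK/PD modeling and clinical development, so a misreading could carry forward. Sections 2.3 and 8.3.8.1 also seem to disagree on whether a platelet response is expected.

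**Working it through.** **The plan's own figure.** Table 7 gives an AUC of 98.5 µg·hr/mL at 25 mg SC.

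- 98.5 / 168 h = 0.586 µg/mL, exactly the value in section 4.2.1.3.3. Over 576 h it would be 0.171, so the window is 168 h.
- 0.586 / 0.25 = 2.3, consistent with the stated factor of about two.

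There is no calculation error.

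**ITP doses against each benchmark.** Cav = AUC / 168, with AUC and Cmax from Table 7. The 168 h window is assumed for 50 and 100 mg, because the column header allows 168 or 576 h.

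| Dose SC | Cav (µg/mL) | Cav / 0.25 | Cav / 37 | 37 / Cav | Cmax / 6 |
|---|---|---|---|---|---|
| 25 mg | 98.5/168 = 0.586 | 2.3 | 1.6% | 63 | 0.895/6 = 15% |
| 50 mg | 159/168 = 0.946 | 3.8 | 2.6% | 39 | 1.37/6 = 23% |
| 100 mg | 315/168 = 1.875 | 7.5 | 5.1% | 20 | 2.64/6 = 44% |

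The benchmarks differ by 37 / 0.25 = 148, or by 6 / 0.25 = 24 if the trough target is used.

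**Can both figures be valid?** Under simple binding, occupancy = C / (C + Kd), so 90% occupancy needs C = 9 × Kd.

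- Occupancy of at least 90% at 0.25 µg/mL needs Kd ≤ 0.25 / 9 = 0.028 µg/mL.
- Section 2.2.1 reports an apparent Kd of at most 1.45E-10 M on recombinant human Fcγ receptors. Then 9 × Kd = 1.3 nM. The molecular weight is not given. Assuming 60 to 300 kDa, 1.3 nM is 0.08 to 0.39 µg/mL, a range that contains 0.25.
- The approximately 1% occupancy in section 4.2.1.3.1 uses the whole-blood B-cell Kd of 13.95 µg/mL: 0.17 / (0.17 + 13.95) = 1.2%. The same Kd gives 0.586 / (0.586 + 13.95) = 4.0% at the 25 mg average.

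The two occupancy statements can therefore coexist if they come from different assays. The text does not make that link, so it is an inference.

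**Does the bracketing sentence fail?** Table 8 lists IV doses up to 16 mg/kg. From Table 6, the average at 1 mg/kg is 490 / 168 = 2.92 µg/mL. Assuming dose proportionality, 16 × 2.92 = 46.7 µg/mL, above 37. The planned IV range did bracket the target. Section 2.1 explains why it was not reached: a maximum tolerated dose of 0.3 mg/kg was identified and IV dosing ended.

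**What does 37 µg/mL predict at the ITP doses?** If 37 is the IC90, the fraction of maximal effect is 9(C/37)^h / [1 + 9(C/37)^h]. The Hill coefficient h is not given, so a range is shown.

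| h (assumed) | 25 mg | 50 mg | 100 mg |
|---|---|---|---|
| 0.5 | 53% | 59% | 67% |
| 1 | 12.5% | 18.7% | 31.3% |
| 2 | 0.2% | 0.6% | 2.3% |

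The prediction at 25 mg runs from almost nothing to more than half of the maximal effect.

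**The case for a change.** The strongest case for acting is that section 2.1 treats platelet response as a validated marker and as informative for development, yet nothing visible says which exposure expectation applies in ITP. Cohorts 13 and 14 are listed as not dosed in Table 4, so an interpretation could still be written down beforehand. An exposure-platelet plot would need no new samples. The occupancy figures add to the awkwardness: about 1% at a predicted 0.17 µg/mL in one section, and at least 90% at 0.25 µg/mL in another.

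Part of this stands. Section 4.2.1.3.3 does not name the assay behind 0.25 µg/mL or relate it to 37 or 6 µg/mL. The occupancy label in section 4.2.1.3.1 is also looser than the B-cell wording in section 2.2.3.

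The claim of two opposite readings does not stand. Section 2.1.1 says that no single pathway can be identified as responsible for clinical efficacy, so a flat response at high Fcγ occupancy would not by itself refute the mechanism. On the 37 µg/mL basis, whether a flat response is informative depends on an unknown Hill coefficient. It also depends on an averaging interval and regimen that section 4.2.1.2 does not state. Under either benchmark, a few open-label participants, some on permitted background ITP drugs, give weak evidence.

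Sections 2.3 and 8.3.8.1 scarcely conflict. The first says a transient rise is possible; the second explains why a subsection on reporting lack of efficacy does not apply. Nor can absence of pre-specification be shown, because parts of the objectives and of section 9.6 are redacted. That the supplied SAP describes only IV dosing in healthy subjects is a separate matter.

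**Conclusion.** No change to the plan follows. The 148-fold gap and the 1.6% to 5.1% figures are correct, given a 168-hour average for all three doses, but they compare receptor occupancy with a concentration for 90% effect in a mouse arthritis model. Both can be true at once.

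Neither benchmark does any work in the plan. The ITP starting dose rests on safety and tolerability in healthy participants. Dose progression and escalation in sections 6.6 and 6.7 run on adverse events, platelet falls and PK limits of 1130 µg/mL and 34000 µg·hr/mL. The primary and PK analyses use neither 0.25 nor 37 µg/mL.

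The protocol makes no efficacy claim, already lists and summarizes individual platelet counts, and foresees PK/PD modeling. An analyst with those data and the scheduled PK samples can plot platelet change against exposure and report a flat result as no rise seen up to the exposures reached, without a prior rule. A sentence naming the assay behind 0.25 µg/mL would help a reader, but it would alter no result. This view rests on the visible text and on simple binding; the molecular-weight range and Hill values are assumptions used only to show that the two benchmarks need not conflict.
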